	4.1 Study Summary				
	4.2	Study	Population:	14	
5	STUDY ENROLLMENT AND WITHDRAWAL				
	5.1	Subjec	ct Inclusion Criteria	16	
	5.2	-			
6	STATISTICAL CONSIDERATIONS				
	6.1	Justification of effect size			
		6.1.1	· iis signissi		
		6.1.2	Minimum Clinically Important Difference		
		6.1.3	3		
		6.1.4			
7	LITER	RATURE	REFERENCES	20	

4/24/19

LIST OF ABBREVIATIONS

AE Adverse Event/Adverse Experience

BMI Body Mass Index CC Clomiphene Citrate

DHEA-S Dihydroepiandrosterone sulfate

DHHS Department of Health and Human Services

FDA Food and Drug Administration
IRB Institutional Review Board

IRL Iowa River Landing

PCOS Polycystic Ovary Syndrome

PPCOS II Pregnancy in Polycystic Ovary Syndrome Study II

P4 Progesterone

PI Principal Investigator

SAE Serious Adverse Event/Serious Adverse Experience

UIHC University of Iowa Hospitals and Clinics

US United States

PROTOCOL SUMMARY

Title: Combined Letrozole and Clomid in Polycystic Ovary

Syndrome: A randomized control trial of combination of letrozole and clomiphene citrate or letrozole alone for the

treatment of infertility in women with polycystic ovary syndrome

Précis: This will be a single center, randomized controlled open trial of

letrozole versus letrozole and clomiphene citrate (CC) for one cycle. Women will be randomized in a 1:1 ratio to receive letrozole 2.5 mg or combination of letrozole 2.5 mg and clomiphene 50 mg for 5 days on days 3-7 of menstrual cycle. We will stratify the randomization by age (< 35 versus >35) and BMI (<30, > 30) to try to ensure equal groups to study. The women and their partners will be instructed to have regular intercourse with the intent to conceive during the cycle. Patients will have an ultrasound on between cycle day 12 -14 and will evaluate number of follicles (>15 mm), follicle size, endometrial thickness and pattern. Patients will have midluteal phase progesterone level drawn. The primary analysis

ovulatory rate in the two treatment arms.

Objectives: Primary: Cumulative ovulation rate determined by a mid-luteal

(day 21) phase progesterone level. Progesterone level > 3

will use an intent-to-treat approach to evaluate differences in

ng/mL will indicate ovulation.

Secondary: Size and number of developing follicles, endometrial thickness and pattern all determined by a midcycle ultrasound. Positive pregnancy test, clinical pregnancy and ongoing pregnancy. We will also report live birth rate, miscarriage rate, ectopic pregnancy rate and multiple pregnancy rate. We will also monitor complication rate and

side effect profile of both treatment arms.

Population: 70 women with a diagnosis of polycystic ovary syndrome and

infertility desiring to conceive. Participants will be 18-40 years

of age.

Phase: IV

Number of Sites: 1 – University of Iowa Hospitals and Clinics, Women's Health

Clinic and Quad Cities clinic

[figure not shown]
Description of Intervention:

70 women will be equally randomized to two different treatment arms: A) letrozole 2.5 mg every day for 5 days (day 3-7 of cycle) or B) letrozole 2.5 mg and clomiphene citrate 50 mg every day for 5 days (3-7 of cycle), for one cycle.

Subject Participation Duration: Approximately 5 weeks of active participation time. Clinical chart abstraction and remote follow up will be continued for 10 months following participation.

Estimated Time to Complete Enrollment:

18 months by enrolling ~3.89women per month

2 INTRODUCTION: BACKGROUND INFORMATION AND SCIENTIFIC RATIONALE

2.1 Background Information

Polycystic ovary syndrome (PCOS) is the most common endocrine disorder in reproductive age women and constitutes the most common cause of anovulatory infertility. The treatment of infertility in patients with PCOS focuses on ovulation induction. Multiple treatment regimens have been used and all with varying success in regards to both ovulation and pregnancy rates.

Clomiphene citrate (CC) is a commonly used pharmacologic agent to induce ovulation in women with PCOS. It works as a selective estrogen receptor modulator (SERM) by competitively attaching to nuclear estrogen receptors. As the negative feedback of estrogen is lowered it in turn activates increased secretion of gonadotropin hormones which subsequently causes ovarian follicular growth. CC also has an antiestrogenic effect on endometrial development and cervical mucus production. This has been implicated to contribute to the low pregnancy rate despite a relatively high ovulation rate. ^{2, 3} Letrozole has a different mechanism of action and works as a highly selective aromatase inhibitor thus preventing androgen-to-estrogen conversion. The negative feedback in the hypothalamus is decreased by the suppressed estrogen production which subsequently increases the concentration of follicle stimulating hormone (FSH). An additional mechanism of aromatase inhibitors may result from increase follicular sensitivity to FSH resulting from temporary increased intraovarian androgens. 4 Studies in primates have shown that testosterone augments follicular FSH receptor expression which supports the idea that androgens promote follicular growth. 5-7 Additionally, Garcia-Velasco et al demonstrated an increase in intraovarian androgen concentrations with the use of letrozole in low responder patients undergoing IVF.8 Letrozole offers a benefit over CC for ovulation induction since it does not deplete estrogen receptors in both central and peripheral target tissues and normal central feedback mechanisms remain intact. Recently, a randomized control trial comparing letrozole to clomiphene demonstrated that letrozole was associated with higher live-birth rate (27.5% vs 19.1%, P=0.007, 95% CI 1.10 to 1.87) and cumulative ovulation rate (61.7% vs. 48.3%, P<0.001) among women with polycystic ovary syndrome. 9 Despite the superior ovulatory and live birth rates with letrozole compared to CC the question remains if there are medical alternatives without proceeding to gonadotropins or IVF both of which are associated with increased costs and risks.

Since letrozole and CC have different mechanisms of actions we postulate that the combination of these medications may offer a synergistic effect and improve the ovulatory rate. One study has prospectively reviewed treatment outcomes using a combination of letrozole and clomiphene who had previously failed CC for 6 cycles and letrozole for 4 cycles. This study enrolled 100 patients and showed an ovulatory rate based on development of dominant follicle of 82.9% of cycles (213/257) with the combination treatment. However, this study was not randomized and used a limited population of women with PCOS that were resistant to both clomiphene and letrozole alone. Additionally, patients received Gonal-f on day 11 if a dominant follicle was present and then received hCG trigger when the follicle was >18 mm in size

followed by IUI 36-38 hours later. Despite the prospective observational nature of the study it does point to a potential improved ovulatory rate with this combination treatment.

2.2 Rationale

Letrozole has been shown to have both higher live-birth and ovulation rates compared to CC among infertile PCOS women demonstrated by the PPCOS II trial. Despite the superior ovulatory and live birth rates with letrozole compared to CC the question remains if there are medical alternatives without proceeding to gonadotropins or IVF both of which are associated with increased costs and risks. One study has shown a potential benefit in combining letrozole and CC however a double blind trial is needed to test if this combination improves outcomes over letrozole alone.

Mechanistically, the combination may have a synergistic action with letrozole having a local effect at the level of the ovary to block estrogen synthesis and with clomiphene having a central effect by antagonizing the negative feedback of estrogen at the hypothalamus by depleting estrogen receptors. These different mechanisms of actions may provide a synergistic effect to provide improved ovulation rates over use of letrozole alone. Since the combination of letrozole and clomiphene has not yet been studied in a prospective randomized fashion and it is unclear if this will offer an advantage over letrozole alone in terms of both ovulation and pregnancy rate, we have designed a pilot study to characterize the ovulatory rate with this combination treatment. It is necessary to first determine if the combination treatment is at least equivalent and possibly better than the standard efficacy of letrozole. Prior to embarking on a larger trial to look at the most important outcome of live birth rate it is important to establish that this combination treatment does offer a superior ovulatory rate. The aim of this study is to test the hypothesis that combined therapy of letrozole and CC is an effective and superior method to letrozole alone to achieve ovulation in women with PCOS.

2.3 Potential Risks and Benefits

2.3.1 Potential Discomforts & Risks

Both letrozole and CC have are used for the treatment of infertility. Below is a table listing all tests or procedures involved in this research study and their related discomforts and risks.

Test or Procedure

Discomfort and Risks

Other dead and are shown for bland Olimbia single and in confert horizing at the site of				
Standard venipuncture for blood	Slight pinch or discomfort, bruising at the site of			
work	puncture, small blood clot, infection or bleeding at the			
	site, and fainting during the procedure			
Transvaginal ultrasound	Abdominal or pelvic discomfort			
Clomiphene Citrate	Hot flashes, visual changes (blurring of vision, double			
	vision, floaters), abdominal pain, nausea, vomiting,			
	constipation, mood changes, headache, fatigue, multiple			
	pregnancies, formation of ovarian cyst, breast			
	discomfort, abnormal uterine bleeding, bloating,			
	formation of ovarian cysts			
Letrozole	Fatigue, dizziness, nausea, hot flashes, discomfort in			
	your joints, back pain, increased cholesterol levels,			
	formation of ovarian cysts, multiple pregnancies			

^{*} Table is modified from PPCOS II trial

It is expected that patients will not experience all of these side effects. Side effects associated with medications are temporary and manageable.

Although the goal of treatment is to achieve pregnancy, there is no guarantee that treatment will result in pregnancy or a live birth. CC has been associated with a 5-8% multiple pregnancy rate and Letrozole is associated with a 3.4% multiple pregnancy rate in women with PCOS. The multiple pregnancy rate of the combination of these treatments is unknown. Multiple gestations are associated with preterm labor and delivery as well as most pregnancy complications including diabetes and high blood pressure.

If pregnancy occurs it is possible that the pregnancy results in a non-viable pregnancy or tubal (ectopic) pregnancy. In either of these cases occur, further medial or surgical treatment may be necessary.

The incidence of congenital anomalies in the general population is 3% to 5%. In the PPCOS II trial comparing letrozole and CC there were a total of 5 congenital anomalies (1/66 in CC group – 1.5%, 4/102 in letrozole group 3.9%).⁹

2.3.2 Potential Benefits

Possible benefits to participants: The potential benefit to the participants is that they will receive a treatment (letrozole) that is known to improve ovulatory and pregnancy rates in women with infertility and PCOS compared to no treatment at all or CC alone. The participant may receive a treatment (letrozole + CC) that may prove to be more effective than letrozole alone. Treatments may result in pregnancy although this cannot be guaranteed.

With the mid-cycle ultrasound and hormone testing the participant may receive additional information and understanding related to their cause of infertility.

Possible benefits to others: The study will provide important information on the treatment for women with infertility and PCOS. This will provide knowledge on effective ovulation treatments for this patient population. The knowledge gained from this research may help discover an effective and safe way to achieve ovulation and pregnancy.

3 OBJECTIVES

3.1 Primary research hypotheses

Treatment with the combination of letrozole and clomiphene is more likely to result in ovulation (increased ovulation rate) compared to treatment with letrozole alone in women with infertility and PCOS.

3.1.1 Primary Outcome measures

The primary outcome measure is the occurrence of ovulation defined as a mid-luteal progesterone level > 3 ng/mL. This will be tested 7 days following the patient reporting of an LH surge. If no LH surge is detected the lab will be drawn on cycle day 21 or 22. The primary analysis of ovulation rate within the two treatment conditions will employ an intent-to-treat approach.

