3.2 Secondary outcomes

We will analyze secondary outcomes however due to sample size will not be able to power differences in pregnancy rate and live birth rate. Descriptive secondary outcomes will include positive pregnancy test, clinical pregnancy, and ongoing pregnancy. We will also evaluate number and size of developing follicles determined by ultrasound, endometrial thickness and pattern by ultrasound. We will also monitor adverse events during treatment and side effect profile of both treatment arms.

We will evaluate pregnancy outcomes and report any fetal anomalies.

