4 STUDY DESIGN

Treatment Design: This will be a single center, open trial of oral letrozole vs. combination of oral letrozole and clomiphene citrate in the treatment of infertility in patients with polycystic ovary syndrome. Patients will be randomized to receive either a dose of 2.5 mg of letrozole or 2.5mg of letrozole and 50 mg of CC for 5 days on cycle days 3 through 7 of the menstrual cycle. Patients will be monitored during the cycle with a mid-cycle ultrasound (cycle days 12-14) and a mid-luteal progesterone level (cycle day 21).

The study will last for -1 cycles or approximately -5 weeks.

Randomization will be stratified by age (< 35 versus \geq 35) and BMI (< 30 and \geq 30) to ensure equal groups to study. Randomization will be via a computer based central randomization to ensure adequate allocation concealment.

Enrollment will take approximately 18 months if ~ 3.89subjects are enrolled per month. Active subject participation will be through completion of -1 cycle. We will follow up with patient regarding pregnancy, delivery outcomes, and if information is not available via chart abstraction.

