4.1 Study Summary

Initial visit:

- 1. Study staff review pre-screening questionnaire and confirm eligibility criteria
- 2. Obtain signed informed consent
- 3. Confirm documentation of vital signs, height, weight and BMI.
- 4. Record and review medical history
- 5. Request subject to sign medical release form to obtain information regarding ongoing infertility treatment, pregnancy and delivery information.
- 6. Complete urine pregnancy test or dispense urine pregnancy test to complete at a later date if participant plans on delaying treatment.
 - 7. Randomization to treatment group once negative pregnancy test.

- Orient and dispense calendar log which includes documentation of intercourse, menstrual log and side effect assessment
 - Dispense study medications

Mid-cycle Visit (Visit #2):

- 1. Collect journal logs
- 2. Transvaginal ultrasound exam
- 3. Return medication containers and study medications you did not take
- 4. Dispense urine pregnancy test

Mid-luteal lab draw (visit #3)

- 1. Blood draw (P4)
- 2. Schedule End of treatment visit

End of Treatment Visit:

- 1. Collect Calendar log
- 2. If subject had a positive urine pregnancy test: blood draw will be performed and then repeated approximately 48 hours after the first one.
 - 3. Complete End of Treatment questionnaire
- 4. Arrange for follow up and confirm we have a release of records for pregnancy and neonatal records.

4.2 Study Population:

70 women with PCOS actively seeking pregnancy (or 35 per each treatment arm) aged \geq 18 to \leq 40 years will be enrolled. The overall goal of enrollment criteria is to identify a population of healthy women with PCOS and infertility not specified by another cause. Infertility will be determined by clinical history. PCOS will be determined by Rotterdam criteria which includes two of three findings: oligo- or anovulation, hyperandrogenism or polycystic ovaries on ultrasound.

- Hyperandrogenism will be determined by evidence of hirsutism on exam or by biochemical elevations in total testosterone.
- Ultrasound findings of polycystic ovaries including ≥ 12 follicles of 2-9 mm diameter or increased ovarian volume (>10 cm³) in either ovary.

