6 STATISTICAL CONSIDERATIONS

6.1 Justification of effect size

6.1.1 Prior Studies

The primary outcome is ovulation, defined by a mid-luteal progesterone level > 3 ng/mL. There is data demonstrating the cumulative live birth rate with clomiphene and letrozole from the PPCOS II trial. This trial compared letrozole to clomiphene demonstrated that letrozole was associated with a higher cumulative ovulation rate (61.7% vs. 48.3%, P<0.001) among women with polycystic ovary syndrome and the rate of ovulation after one treatment cycle with letrozole 2.5 mg was 50%.9 Unfortunately, there is no comparative quality data from randomized trials of the combination of letrozole and CC. There is one study that prospectively reviewed treatment outcomes using a combination of letrozole and clomiphene who had previously failed CC for 6 cycles and letrozole for 4 cycles. This study enrolled 100 patients and showed an ovulatory rate (defined by development of dominant follicle) of 82.9% of cycles (213/257) with the combination treatment. 10 However, this study was not randomized and used a limited population of women with PCOS that were resistant to both clomiphene and letrozole alone. Additionally, patients received Gonal-f on day 11 if a dominant follicle was present and then received hCG trigger when the follicle was >18 mm in size followed by IUI 36-38 hours later.

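### Ovulation is defined by progesterone above 3 ng/mL alone, so a woman who conceives in the study cycle with a lower value is coded as not ovulating; the draw-day wording also needs reconciling (minor)

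*Combined protocol and SAP*

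**What the plan says.** **Definition.** Section 3.1.1 reads: "The primary outcome measure is the occurrence of ovulation defined as a mid-luteal progesterone level > 3 ng/mL". Section 6.1.1 repeats it: "The primary outcome is ovulation, defined by a mid-luteal progesterone level > 3 ng/mL". The Objectives entry of the Protocol Summary uses the same cut-off. Section 6.1.3 names the Pearson chi-square test on an intent-to-treat basis and adds no rule for deriving the outcome.

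**Pregnancy.** Section 3.2 treats pregnancy separately: "Descriptive secondary outcomes will include positive pregnancy test, clinical pregnancy, and ongoing pregnancy". Section 4.1 provides a urine test and, if it is positive, two blood draws about 48 hours apart. No analyte is named for those draws.

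**Timing of the progesterone draw.** Section 3.1.1 has two branches: "This will be tested 7 days following the patient reporting of an LH surge", and "If no LH surge is detected the lab will be drawn on cycle day 21 or 22". The Protocol Summary gives a single day, "day 21) phase progesterone level", as does section 4, "a mid-luteal progesterone level (cycle day 21". Section 4.1 lists the draw without a day. It describes the participant's record as a "calendar log which includes documentation of intercourse, menstrual log and side effect assessment" and does not mention LH testing or a surge date.

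**The concern.** The hypothesis in section 3.1 is about ovulation, and progesterone is the marker for it. Conception in the study cycle shows that ovulation took place, whatever the progesterone value. A rule based on progesterone alone sets that evidence aside, and the same woman would then appear as anovulatory in the primary table and pregnant in a secondary one.

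Draw timing bears on this. If a woman surges late and her blood is taken on a fixed day, the sample may precede the rise above 3 ng/mL. An undetected late surge is the most plausible route to a low value in a woman who conceives. Eligibility rests partly on oligomenorrhea or chronic anovulation (section 5.1), so regular cycle timing cannot be presumed.

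At stake is the coding of very few women. However, the trial is small and open-label. If such a case arose without a rule written beforehand, someone would have to decide how to handle it with the arm known.

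**Working it through.** **1. The plan's own figure.** The documents give no figure for conceptions with low progesterone. The only related figure is the sample size in section 6.1.4, which uses rates of 0.50 and 0.83 at two-sided 0.05.

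n per arm = [1.96 × √(2 × 0.665 × 0.335) + 0.842 × √(0.50 × 0.50 + 0.83 × 0.17)]² / 0.33² = [1.308 + 0.526]² / 0.1089 ≈ 30.9, rounded up to 31.

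Power at 31 per arm is 0.801. Allowing for 10% dropout, 31 / 0.90 = 34.4, rounded up to 35. The figure reproduces, and this point does not dispute it.

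**2. How many women might be miscoded.**
- From the documents: 70 women (section 4.2), a live-birth rate of 27.5% on letrozole in the earlier randomized trial (section 2.1), and 5 cycles in that trial (section 6.1.4).
- Assumed: births spread evenly over the cycles; the same rate in both arms; 1.5% to 15% of these women sampled too early to exceed 3 ng/mL; and, as a variant, twice as many pregnancies as live births.

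Live births from one cycle in the whole trial: 70 × 0.275 / 5 = 3.85.

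| Assumed share sampled too early | Count 3.85 | Count doubled, 7.70 |
|---|---|---|
| 1.5% | 0.06 | 0.12 |
| 4.5% | 0.17 | 0.35 |
| 15% | 0.58 | 1.16 |

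The expected number in the whole trial is therefore 0.06 to 1.16.

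**3. Whether one woman can matter.** Uncorrected chi-square, with illustrative counts of ovulating women:

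| Per arm | Counts | p |
|---|---|---|
| 31 | 16 vs 24 | 0.034 |
| 31 | 16 vs 23 | 0.066 |
| 35 | 18 vs 26 | 0.048 |
| 35 | 18 vs 25 | 0.086 |

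One recoding can move a result across 0.05, but only if the result is already close to it. These are not forecasts.

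**4. The timing statements side by side.** Under section 3.1.1 the draw day is the surge day plus 7.

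| Situation | Section 3.1.1 | Protocol Summary and section 4 | Gap |
|---|---|---|---|
| Surge on day 14 | day 21 | day 21 | 0 days |
| Surge on day 18 | day 25 | day 21 | 4 days |
| No surge detected | day 21 or 22 | day 21 | 0 or 1 day |

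The statements agree for a day-14 surge and for a no-surge draw on day 21. They differ for every other surge day.

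**The case against.** **The rule is already complete.** The same objective cut-off appears in three places, section 5.1 uses a value of 3 ng/mL for chronic anovulation, and every woman with a result can be coded. On this view a pregnancy clause is a design preference. The rule is indeed unambiguous. But in the case described it returns an answer known to be wrong for the stated hypothesis, which is more than a matter of taste.

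**The size is built on assumptions.** This stands. The documents support neither the 1.5% to 15% range nor the doubling. The early-draw route also mainly concerns women with no detected surge, because section 3.1.1 ties the draw to the surge when one is reported.

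**Adding pregnancy has its own cost.** This also stands. Only women who conceive are corrected. Section 2.1 says clomiphene's antiestrogenic effect on endometrium and cervical mucus has been implicated in a low pregnancy rate despite a relatively high ovulation rate. If conception per ovulation differs by arm, the correction would too. Keeping progesterone alone as primary and using the wider definition as a sensitivity analysis is a reasonable alternative. Against that, a pregnancy properly attributed to the study cycle cannot be a false positive for ovulation.

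**The day-21 statements are shorthand.** They may well be: they are parenthetical remarks in a synopsis and a design overview, and section 3.1.1 is the section that defines the outcome. They do not say so, however. Nor does the silence of section 4.1, a summary, show that surge dates go unrecorded on the study's data forms.

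**Conclusion.** The point holds and is minor. As written, the primary definition counts a woman who conceives in the study cycle with progesterone of 3 ng/mL or less as not ovulating, and nothing in the documents available for review overrides it. The number is unknown. On the assumptions above it is probably none or one in 70.

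A reader might infer more, and the documents do not support it:
- **That the primary endpoint is invalid or the trial's power is in doubt.** Nothing shows that such conceptions are more than rare, and the sample size reproduces.
- **That the draw is timed differently in the two arms.** No section gives an arm-specific rule.
- **That the timing statements never agree except for a day-14 surge.** They also agree for a no-surge draw on day 21, a branch that may cover many women.

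The timing difference is a matter of wording to reconcile. It is not evidence that blood will be drawn on the wrong day.

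**What to change.** **1. Outcome definition (sections 3.1.1 and 6.1.1, Protocol Summary).** Count as ovulation a mid-luteal progesterone above 3 ng/mL or a confirmed pregnancy from the study cycle. State what confirms the pregnancy, since section 4.1 does not name the test on the follow-up blood draws. Report progesterone alone as a sensitivity analysis, and report by arm how many women the pregnancy clause reclassified.

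*Cost:* a short text change, with no extra visits or blood draws. The endpoint is no longer progesterone alone. Late ovulators who do not conceive and have no detected surge stay misclassified. The correction may differ slightly between arms, which is why reclassified women should be shown by arm.

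**2. Draw timing (Protocol Summary, sections 3.1.1, 4 and 4.1).** Reconcile the statements to one rule. Record the surge date, or that no surge was detected, together with the draw date.

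*Cost:* an edit for consistency and one or two data fields, if the forms do not already hold them.
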